Additional details are also available in the published study protocol.² Baseline characteristics at the time of randomization will be computed for each treatment group (REDvent and usual care) and within each phase (Acute and Weaning). For all analyses, assumptions for data distribution will be assessed, and normalizing transformations of the data or nonparametric analysis will be performed as necessary. The mean and standard deviation will be reported for normally distributed continuous variables, and the median and interquartile ranges will be reported for non-normally distributed continuous variables. Given this is an RCT, we anticipate balanced baseline characteristics. To evaluate this, we will calculate effect sizes for measures of central tendency (Cohen d, Cramer v) across groups. For non-parametric

variables, effect sizes defined for the Mann-Whitney U will be calculated to produce r . For frequency counts and percentages the rate ratio will be evaluated to calculate the effect size. Variables that have more than a small effect size ($d > 0.2$, $v > 0.01$, or $r > 0.1$, categorical effect size >1.2) indicate potential imbalances in baseline characteristics between groups. These variables will be included in sensitivity analyses after the primary ITT analyses are performed or included as covariates using multivariable models.

Retention, adherence, and missing data will be compared across groups. High levels of missing data are not anticipated given the nature of the study. If the missing data are determined to be related to the outcome (not missing at random) or related to group or a covariate (missing at random), we will explore the impact of these biases in sensitivity analyses after the primary ITT analyses using multiple imputation processes. Our primary approach to imputing missing data is the Markov Chain Monte Carlo (MCMC) simulation. Statistical Analysis Software (SAS) procedures will be used.

The primary analysis seeks to address if there are differences in length of weaning between: 1) REDvent-acute compared to usual care acute, 2) REDvent-weaning compared to usual care-weaning, and 3) REDvent-acute and weaning (combined) compared to usual care acute and weaning (combined). Analyses of these aims will follow the ITT principle. The primary analyses will compare median weaning duration between groups using a Mann-Whitney U test, or a t-test with transformation as necessary. The effect size (r) will also be computed to assess the magnitude of treatment effect. If imbalances in baseline characteristics are found between or across randomized treatment groups, a Cox proportional hazard model will be performed to adjust for covariates. The estimates (mean, median, or hazard ratio) and the associated 95% confidence interval, as well as the p-values, will be presented for interpretation.

Power analysis: For the primary outcome (weaning duration), a 1-day change in length of weaning is considered clinically significant. It is anticipated that up to 20% of patients may not achieve the primary outcome (successful passage of an SBT or extubation due to death or dropout); these patients will not be included in the primary outcome analysis but will be included in secondary outcomes. We are targeting an overall sample size of 300 patients, with a minimum of 240 patients (120 per arm) available for analysis of the primary outcome. Using the planned statistical tests above, this sample size would be able to detect a ≥ 1 -day change in weaning duration with a two-sided alpha of 0.05 and power of 0.9, or a relative hazard ratio of 1.5 (ratio between control/intervention group) with a power of 0.9 or a hazard ratio of 1.4 with a power of 0.8. Patients who fail the initial SBT will undergo the weaning phase randomization. From our pilot data, approximately 25% of patients exposed to the intervention passed the initial SBT. Anticipating 180 patients (90 per arm) will receive weaning phase interventions, there will be adequate power to detect a ≥ 1 day change in the length of the weaning phase, or a hazard ratio of 1.5 with an alpha of 0.05 and power of 0.8 in the weaning phase.

The analytic approach for secondary aims and outcomes such as mortality and ventilator free days will follow those described above. For categorical data, a χ^2 or Fisher's exact test will be used to compare difference between groups. Logistic regression will be used to assess binary outcomes, and a multinomial/ordinal logistic regression will be used for categorical outcomes (> 2 categories) while adjusting for covariates. To assess the association between 2 continuous variables, a Pearson or Spearman correlation will be used, and analysis of covariance (ANCOVA) will be used to adjust for covariates. Generalized Estimating Equations (GEE) or mixed effect models will be used when necessary to analyze repeated measures. Because of the physiologic nature of the study with a Phase II design,

multiple comparisons adjustment is not planned for secondary outcomes. Analyses will be performed using the appropriate recent version of the SAS statistical software (SAS Institute Inc., Cary, NC).

In order to increase precision around the effect estimates for the primary and secondary aims and to reflect the stratified sampling, all analyses are adjusted for block randomization variables.³ For acute phase these are age group (infant, child, and adolescent) and whether or not the subject was immunocompromised. For the weaning phase this is acute phase randomization grouping and age group. In addition, variables thought to be potential confounders on the relationship between intervention and outcome with large differences between groups (standardized effect sizes as detailed above) will also be included in all adjusted analyses. Unadjusted analyses will be presented to summarize data; all primary and secondary outcomes will present adjusted analyses controlling for age category, immunosuppression and imbalanced baseline variables. Potential confounders will be assessed for multicollinearity and if present, the confounder with the highest biological plausibility to impact the effect of the intervention on the outcome will be selected for inclusion as a model covariate.

Model assumptions and fit for multiple linear regression (with or without log transformation) will be assessed visually for normality of residuals as well as variance inflation factor and difference in betas (DFBETAS) for influential points. Model fit for binary multiple logistic regression will be assessed with Pearson Chi-square and deviance. Firth's penalized likelihood method will be used in subgroup analyses when event rates are small to reduce bias in the parameter estimates.⁴ When using negative binomial regression, model fit will be assessed for over and underdispersion with the scaled Pearson Chi-square/deviance and influential points assessed as previously described. The proportional hazards assumption will be assessed when using Cox proportional hazards modeling using graphical approaches ("log-log" figures and Kaplan-Meier curves) for each covariate. Repeated measures analysis for ventilator settings, lung mechanics, and respiratory measures will be assessed with linear mixed models and generalized linear mixed models that include a variable for time from randomization to control for correlation of values within each patient using the first-order autoregressive structure. The robust sandwich estimators for standard errors will be used to reduce heteroscedasticity when appropriate.

A detailed outline of each outcome's analysis approach to control for blocking variables and confounders is given in the Table 1. Pre-specified comparisons of interest are REDvent acute vs. usual care acute, REDvent weaning vs. usual care weaning, and four group combination: 1) REDvent acute + REDvent weaning 2) REDvent acute + usual care weaning 3) Usual care acute + usual care weaning 4) usual care acute + REDvent weaning. The four group combinations comparisons are exploratory and will only be considered if there are noted differences between both acute and weaning phase interventions.

October 2019- new milestone accrual plan

After the first 75 patients were enrolled in the study a new milestone accrual plan was created to account for the increase in the percentage of patients meeting the primary outcome. Previously, it was assumed 20% of patients would not meet the outcome, however, data after 75 patients revealed this was 13% and the total sample size requirement was adjusted down from 300 to 276 patients. The number of patients targeted per group to meet the primary outcome was unchanged, at 120 per group. This updated milestone accrual plan was reviewed and accepted by the NLHBI and DSMB.

January 2023 - Change in primary analysis for length of weaning

Blinded, non-inferential summary statistics and distributions were assessed for the length of weaning outcome by the primary statistician as part of the data cleaning process. It was revealed that length of weaning might not be optimally analyzed as a continuous variable because SBTs were conducted once a day, with most patients passing their SBT within the first three days. In addition, enrollment had been affected by the COVID-19 pandemic and a new milestone accrual plan was requested by the NHLBI. As the observed distribution appeared more count-like, the primary analysis model was changed to Poisson or Negative binomial regression to better fit the data and satisfy assumptions. This decision was made by the senior biostatistician who was blinded to the randomization groups.

The sample size was re-estimated based on a minimum detectable difference for a reduction in the number of weaning days in the REDvent-acute vs. usual care-acute group using negative binomial regression. This yielded a minimal sample size of 230 patients to detect a reduction of 0.36 to 0.75 days when usual care had an average number of weaning days between 1 and 4, respectively with a power of 80%. This estimate of 230 patients accounted for the 13% loss in those meeting the primary outcome. This updated sample size estimate was reviewed and accepted by the NHLBI and DSMB. Based on this, the milestone accrual plan was revised, and enrollment was planned to continue through March 2024 with a target sample size between 230-276.

May 2024 – Change in primary analysis for length of weaning and PiMax

Data collection and cleaning were completed at the end of May 2024. During the analysis phase, the unblinded statistician checked assumptions and diagnostics for the primary analysis using negative binomial for outcome length of weaning. During this process two influential outliers were discovered in the usual care group who had attempted a SBT but never had a successful SBT; these two patients remained on IMV at 90 days. These patients were eligible for the primary outcome analysis, so were not removed from analysis, however, they were very influential and biased the estimate for the difference in length of weaning days.

Three sensitivity analyses were proposed to address these outliers: 1) truncate length of weaning to 28 days (instead of 90) using log transformed multiple linear regression, 2) categorize length of weaning into clinically relevant groups and conduct a proportional odds logistic regression model, and 3) revert back to the Cox proportional hazards model and censor patients at 28 days. Each of these sensitivity analyses adjusted for the same blocking variables and confounders used in the pre-specified negative binomial regression model. The truncation approaches failed because the assumptions of both log transformed linear regression and time to event analysis were not met. Residuals were highly skewed in linear regression even after truncation and log-transformation. The PH assumption was violated when adjusting for blocking variables when running the Cox proportional hazards model. The proportional odds logistic regression model categorized length of weaning as follows <0.5 day, 0.5 to <1.5, 1.5 to <2.5, 2.5 to <4.5, 4.5 to <7.5, and \geq 7.5 days. Patients who had a long length of weaning were therefore in the highest category of \geq 7.5 days. The proportional odds model uses a rank-based non-parametric approach to model the probability of a lower ordered value, or in our case, a lower length of weaning which can be thought of a latent continuous variable bucketed into meaningful cutoffs. This model also allowed interpretation of the intervention effect on length of weaning in a stepwise manner, which is more representative of what happens clinically with daily SBTs and does not require that the difference between categories be equal. The proportional odds assumption for each independent variable was assessed graphically using their empirical cumulative logits and overall with the score Chi-square test.⁵⁻⁷

Because the pre-specified plan was to use a negative binomial model, those findings have been presented in the main results, but because the model does not appropriately fit the data due to the highly influential outliers, the conclusions and abstract results reflect the more appropriate proportional odds model. This model was agreed upon by the study statistical team and DSMB statisticians in June 2024 at the final DSMB meeting.

PiMax was planned to be modeled with linear regression, with truncation of values >100. In the analysis, no transformation could satisfy the assumptions of linear regression, with poor model diagnostics and non-normality of residuals. PiMax was therefore modeled with the proportional odds model given the non-parametric nature of the data. No specific categories were created for PiMax, but instead it was treated as a rank-based variable with comparisons of ranks between groups, adjusting for blocking variables and confounders (oxygenation index). The model allowed us to compare the odds of a higher PiMax ranking for the REDvent vs. usual care groups. Table 1 has been revised and now presents the description of all outcome variables, initial planned analyses, and modifications to initial proposed analyses and the timing of those changes. In addition, since all outcomes are presented as adjusted analyses, Table 2 details the four main modeling approaches used in these analyses, and interpretation of the model intervention parameter estimates.

References

1. [name] RG, Smith LS, Zimmerman JJ, et al. Pediatric Acute Respiratory Distress Syndrome: Definition, Incidence, and Epidemiology: Proceedings From the Pediatric Acute Lung Injury Consensus Conference. *Pediatric Critical Care Medicine*. Jun 01 2015;16(5_suppl):S23-S40. doi:10.1097/PCC.0000000000000432
2. [name] RG, Hotz JC, Klein MJ, et al. A Phase II randomized controlled trial for lung and diaphragm protective ventilation (Real-time Effort Driven VENTilator management). *Contemp Clin Trials*. Jan 2020;88:105893. doi:10.1016/j.cct.2019.105893
4. Firth D. Bias Reduction of Maximum Likelihood Estimates. *Biometrika* 1993. p. 27-38.

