Consenting subjects will be **block randomized** to intervention or control arms for the acute phase based on age group: infant (30 days -365 days), child (366 days to \leq 8 years), and older child/ adolescent (9-21 years); and immune suppression. For study purposes immune suppressed patients will be defined as: patients with congenital or acquired conditions (including medications) which result in marked inability to respond to antigenic stimuli. Examples of immune suppression include: oncologic disease with recent chemotherapy or radiation, congenital immunodeficiency, HIV, rheumatologic condition on chemotherapy, allogeneic or autologous stem cell transplant, solid organ transplant, or any other condition in which immunosuppressive medications are prescribed. Block randomization will be based on random block sizes of 4, 6 and 8 within the strata above, and loaded into opaque envelopes by the statistician for the study team to determine treatment arm at the time of randomization. Weaning phase randomization will be block randomized by REDvent-acute phase group, age, and immunosuppressed status using the same methodology. Although **blinding** is not possible given the open label nature of the intervention, analysis will be blinded to treatment groups, and performed by an independent statistician.

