D.6.2 Rationale for Randomization Strategy: Age stratified randomization is necessary because *age is an important biological variable* likely to confound the relationship between respiratory muscle weakness and length of weaning. This will ensure an equal age distribution amongst treatment groups. Age groups are based upon accepted pediatric definitions, and have been used in numerous other pediatric RCTs. Neonates (< 1 month) have been excluded because they are often managed with different ventilator strategies and because normal values for PiMax are lower in neonates ^{63, 64}. Immunosuppression is a known risk factor which affects duration of ventilation and weaning, and an imbalance in immunosuppression between groups has been shown to significantly confound previous pediatric mechanical ventilation studies. The additional weaning phase randomization is necessary because we anticipate an imbalance of the number of patients who will be extubated after the acute phase between REDvent-acute and control groups. Acute phase management may have a sustained effect on neuromuscular strength that will affect the duration of weaning. To understand whether the REDvent strategy during the weaning phase can prevent prolonged weaning, risk factors for prolonged weaning (which may be different based on acute phase management) need to be rebalanced with a second randomization. Ultimately, this will allow us to determine the independent utility of REDvent-acute and REDvent-weaning components.

D.6.3 Preparation of the Analysis Data Set

Datasets for analyses consist only of data for which all queries have been resolved. In addition to data management steps to reduce error in data acquisition and entry, a biostatistical cleaning will focus on inconsistencies, missing data and outliers in variables related to the derivation of key outcomes. These activities will be ongoing throughout the study and will involve both the data management team and the biostatistics team.

Preplanned construction of new variables will be conducted in accordance with the study hypotheses and analysis plans. Variable transformation may be required for interpretive

and statistical purposes. With respect to the primary outcome of weaning duration, patients who do not progress to the weaning phase within 28 days (i.e. death, prolonged severe illness) will not be included in analysis of the primary outcome, but will be considered for secondary outcomes.

D.6.4 Statistical Analysis Plan

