2. Supported on MV for pulmonary parenchymal disease (radiographic evidence of alveolar or interstitial opacifications with a clinical risk factor for lung disease e.g. pneumonia, acute respiratory distress syndrome, aspiration, etc.) with Oxygen Saturation Index (OSI= $(\text{FiO}_2 * \text{Mean Airway Pressure} * 100) / \text{SpO}_2$) ≥ 5 or Oxygenation Index (OI= $\text{FiO}_2 * \text{Mean Airway Pressure} * 100) / \text{PaO}_2$) $\geq 4^1$ AND
3. Within 72 hours of initiation of invasive MV

Exclusion Criteria

1. Contraindications to an esophageal catheter (i.e. severe mucosal bleeding, nasal encephalocele, trans-sphenoidal surgery) OR
2. Contraindications to use of Respiratory Inductance Plethysmography (RIP) bands (i.e. omphalocele, chest immobilizer or cast) OR
3. Conditions precluding diaphragm ultrasound measurement (i.e. abdominal wall defects, pregnancy) OR
4. Conditions precluding conventional methods of weaning (i.e., status asthmaticus, severe lower airway obstruction, critical airway, intracranial hypertension, Extra Corporeal Life Support (ECLS), limitation of care, severe chronic respiratory failure, spinal cord injury above lumbar region, cyanotic heart disease (unrepaired or palliated) OR
5. Primary Attending physician refusal

Randomization Strategy and Blinding

For the acute phase, subjects will be block randomized to either arm in a 1:1 allocation ratio, stratified by age group: infant (30 days -365 days), child (366 days to ≤ 8 years), and older child/ adolescent (9-18 years); and immune suppression (congenital or acquired conditions that result in marked inability to respond to antigenic stimuli). Block randomization will use random block sizes of 4, 6 and 8 within the strata above. Weaning phase randomization is block randomized by acute phase group and age, using the same methodology. Although blinding is not possible given the open label nature of the intervention, analysis will be blinded to treatment groups. Randomization schema was loaded into the central REDCAP database by the unblinded statistician. Patients were consented for the study by one of the study investigators, and randomization in the central REDCAP database was conducted by one of the research respiratory therapists or study investigators. Prior to randomization, blocking strata variables were double checked with a second member of the study team or the primary attending physician.

Statistical Analysis Plan

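### The protocol and the SAP disagree on whether immunosuppression is a weaning-phase randomisation stratum, and the final SAP gives two covariate statements for the weaning comparison that do not agree.

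*Combined protocol and SAP*

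**What the plan says.** **Strata for the weaning-phase randomisation.** Section D.6.1 gives three factors in both protocol versions: "Weaning phase randomization will be block randomized by REDvent-acute phase group, age, and immunosuppressed status using the same methodology". The final SAP, under Randomization Strategy and Blinding, gives two: "Weaning phase randomization is block randomized by acute phase group and age, using the same methodology". The Fall 2019 SAP also gives these two. Neither the protocol amendment table nor the SAP summary of changes mentions the strata.

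**Adjustment.** The final SAP's general rule is that "all analyses are adjusted for block randomization variables". It then spells out the blocking variables. For the acute phase they are age group and immune status. For the weaning phase: "For the weaning phase this is acute phase randomization grouping and age group". The paragraph goes on to say that "all primary and secondary outcomes will present adjusted analyses controlling for age category, immunosuppression and imbalanced baseline variables". The Fall 2019 SAP carries both of these specific statements.

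**Why the factor was chosen.** Protocol section D.6.2 says: "Immunosuppression is a known risk factor which affects duration of ventilation and weaning". It adds that imbalance in this factor has confounded earlier paediatric ventilation trials.

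**Age group.** Eligibility in the final SAP runs to 21 years. The protocol's oldest stratum is "older child/ adolescent (9-21 years"); the final SAP still has "older child/ adolescent (9-18 years").

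**The concern.** REDvent-weaning versus usual care is one of the three comparisons listed under the SAP's primary analysis. Tables 1 and 2 of the final SAP describe the models only as adjusted for blocking variables and confounders, so the covariate list depends on the paragraph quoted above. One statement there omits immunosuppression for the weaning phase. The other includes it but does not name acute-phase assignment, which both documents list as a weaning stratum. Neither statement alone contains the protocol's three factors.

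Three things are at stake. One document describes the second randomisation wrongly. If the protocol is right and the explicit weaning-phase statement is followed, a stratification factor believed to be prognostic is missing from the model, and the uncertainty around the weaning effect is overstated. And the final SAP postdates the May 2024 work in which the unblinded statistician was already fitting models, so an ambiguous covariate set leaves a choice that could be made with results in view.

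**Working it through.** The plan gives no figure for this point, so the first step compares the texts.

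| Source | Weaning strata | Number of strata | Average per stratum at N = 180 |
|---|---|---|---|
| Protocol D.6.1 | acute group, age, immunosuppression | 2 × 3 × 2 = 12 | 180/12 = 15 |
| Fall 2019 and final SAP | acute group, age | 2 × 3 = 6 | 180/6 = 30 |

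The 180 is the plan's own number and reproduces: 240 analysable × 0.75 failing the first SBT = 180.

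**Inputs for size.** The prevalence *p* of immune compromise is 0.32-0.39 (protocol B.3.4, Table 1: 32% of historical controls, 39% of pilot patients). The documents give no effect of immunosuppression on weaning duration. I assume *d* = 0.3 to 1.0 residual SD.

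**Case 1: stratified on immunosuppression, left out of the model.** Balance on the factor is built in, but its variance stays in the residual. The reported standard error is too large by about √(1 + *p*(1−*p*)*d*²). Here *p*(1−*p*) = 0.32 × 0.68 = 0.2176, or 0.39 × 0.61 = 0.2379.

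| *d* (assumed) | *p* = 0.32 | *p* = 0.39 |
|---|---|---|
| 0.3 | √1.0196 = 1.01 | √1.0214 = 1.01 |
| 0.5 | √1.0544 = 1.03 | √1.0595 = 1.03 |
| 0.8 | √1.1393 = 1.07 | √1.1523 = 1.07 |
| 1.0 | √1.2176 = 1.10 | √1.2379 = 1.11 |

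**Check by simulation.** N = 180, random blocks of 4, 6 and 8 within the 12 strata, linear model, assumed treatment effect 0.42 SD, 3,000 runs per setting, both prevalences.

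| *d* (assumed) | Type I error, factor omitted | Power, factor omitted | Power, factor included |
|---|---|---|---|
| 0 | 0.050 | 0.81 | 0.81 |
| 0.25 | 0.046 | 0.80 | 0.80 |
| 0.5 | 0.039-0.042 | 0.78 | 0.79-0.80 |
| 1.0 | 0.031-0.037 | 0.73 | 0.80 |

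With the factor included, type I error was 0.046-0.054. Omission therefore makes the test conservative and costs little power unless the effect is large.

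**Case 2: the SAP's six strata were used.** Type I error without immunosuppression in the model was 0.048-0.056, so the analysis is valid. The difference between arms in the proportion immunosuppressed has SD √(4*p*(1−*p*)/180): √(0.8704/180) = 0.070 to √(0.9516/180) = 0.073. That is about 7 percentage points, or roughly ±14 points as a 95% range.

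**Which case applies.** The documents do not settle it. The protocol describes opaque envelopes prepared by the statistician. The final SAP describes a schema loaded into the central REDCap database. The protocol text may be the outdated one, but nothing says so.

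**The case against.** The strongest reply is that nothing in the SAP makes the two adjustment statements rivals. Read together, with the general rule that all analyses adjust for the blocking variables, they give acute group, age and immunosuppression. That reading is available, and it stands against any inference that the SAP simply drops immunosuppression from the weaning analysis. It does not remove the ambiguity, because the only sentence specific to the weaning phase leaves the factor out.

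A reader might also infer that the weaning comparison is not analysed as randomised. The documents do not support that. Analysis is by assigned group under intention to treat, and if the SAP's strata list is the true one, its blocking adjustment matches the randomisation.

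Nor can one say that, without stratification, immunosuppression would be neither balanced nor adjusted for. The SAP also brings in potential confounders that differ between arms, with thresholds of a ratio above 1.2 or Cramér's V above 0.01. A 7-point imbalance around 35% gives 38.5/31.5 = 1.22 and would trigger this rule; a 14-point imbalance gives 42/28 = 1.5. One extra child in 90 gives V of about 0.012. Most chance imbalance would be caught.

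The size rests on an assumed effect. At SD 2.47 days (root mean square of the plan's 2.1 and 2.8), 1 SD is about 2.5 days. That exceeds the pilot difference of 4 − 2.2 = 1.8 days, so it is an outer value. The final models are negative binomial and proportional odds, so linear-model ratios do not carry over exactly; in a proportional odds model, omitting a covariate also changes what the odds ratio estimates.

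Finally, it is tempting to say that patients aged 19-21 have no age group in the model. The adjustment paragraph labels the oldest group only as adolescent, with no upper limit, and the protocol's stratum reaches 21. This looks like a limit left unchanged when eligibility was widened in November 2022.

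**Conclusion.** The point holds as a documentation conflict with a small analytic consequence. The protocol and both SAPs disagree on a stratification factor, no change is logged, and the final SAP's two covariate statements do not agree for the weaning comparison. The conflict dates from the Fall 2019 SAP.

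The consequence arises only if the protocol strata were used and the weaning-specific statement alone is followed. The interval and p-value for REDvent-weaning are then mildly conservative: standard error about 1-3% too large at 0.3-0.5 SD, and up to about 11% at 1 SD. Type I error is not inflated. These figures rest on an assumed immunosuppression effect, the prevalence in the pilot table and a linear-model illustration. The sponsor should resolve it, because it concerns a primary comparison and one covariate set is sound whichever scheme was run.

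**What to change.** 1. In the final SAP's adjustment paragraph, replace the two statements with one rule. Acute-phase models adjust for age group and immunosuppression. Weaning-phase models adjust for acute-phase assignment, age group and immunosuppression. This is valid with 6 or 12 strata.
2. State the weaning-phase strata actually loaded in the randomisation system, and correct whichever of protocol D.6.1 or the SAP's Randomization Strategy and Blinding section is wrong.
3. Change the oldest age group in the final SAP to 9-21 years.
4. If the models already run used a different covariate set, log the change as made after unblinding and show both results.

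The cost is SAP wording, a check of the loaded schema and at most one extra covariate. Immune status is already recorded for every child because it stratifies the acute-phase randomisation in both documents. No patients or procedures are added. If item 4 applies, there is also a second set of results to report.
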